**Assessing the Impact of Herbal Supplement on Fatigue and Disease Activity in SLE:
Results from an 8-Week Randomized Trial**

20-01-2026

Introduction

Systemic lupus erythematosus (SLE) is a chronic auto-immune disease with a wide range of clinical manifestations and a complex pathogenesis. Despite advancements in treatments for disease activity, fatigue continues to be one of the most prominent and unresolved complaints among patients [1].

According to Jianhua Shen et al. [2], fatigue is defined as an overwhelming sense of tiredness, a lack of energy, and a feeling of exhaustion that is associated with impaired physical and/or cognitive functioning. The prevalence of fatigue in SLE may reach up to 90%, according to some studies[3]. Moreover, over 50% of patients report it as their most disabling symptom[3]. Stress, depression, pain, disease activity, and disease duration are among the most common contributors to fatigue in these patients. Fatigue significantly impacts quality of life (QoL) across all domains physical, psychological, and socio-occupational. Management recommendations for fatigue typically involve a combination of pharmacologic and nonpharmacologic approaches; however, no specific medications have been shown to be effective in treating fatigue associated with SLE[4].Hence, it is essential to evaluate and identify potential intervention areas to alleviate patients' symptom burden and enhance their overall quality of life.

Therefore, we opted for the dietary supplement EVACUR.It is a dietary supplement designed to help combat fatigue and boost the immune system. It combines natural extracts, vitamins, and selenium to support overall vitality.

The aim of our double-blind, placebo-controlled randomized trial was to evaluate the efficacy of using herbal-based treatment on patients with SLE-related fatigue .

Methods:

Study Type:

This was a randomized, double-blind clinical trial conducted in two internal medicine departments in Tunisia over a period of 3 months.

Study Population:

Patients with a diagnosis of SLE who were being followed in the participating departments.

Inclusion Criteria:

- Age > 18 years
- Confirmed diagnosis of SLE according to the 2019 ACR/EULAR classification criteria
- Presence of fatigue, defined as a FACIT-F score < 34
- Signed informed consent

Non-Inclusion Criteria:

- Pregnancy or breastfeeding

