- Diseases or comorbidities that may influence fatigue:untreated hypothyroidism, psychosis common infections, and other autoimmune and inflammatory diseases
- Patients on vitamin K antagonist therapy, due to a possible interaction with Ginger and Nigella
- History of severe allergy or intolerance to EVACUR or any component of the placebo

Exclusion Criteria:

- Diagnosis of another systemic disease during the study period
- Pregnancy
- Allergy to any component of EVACUR
- Withdrawal of consent

Data Collection:

Patient data were collected from medical records, including epidemiological characteristics such as age at inclusion, gender and medical and family history. Disease-specific data included the duration of disease,

systemic manifestations, nature of treatment at inclusion. Disease activity was evaluated using clinical SLEDAI-2K score. Baseline FACIT score was collected. Biological assessments were performed such as Anti-dsDNA antibody titers, ANA and serum C3 and C4 levels.

Study protocol:

Randomization:

A two -to-one (2:1) randomization was performed in this study in which patients were randomly assigned into two groups: Group 1 (G1) which received EVACUR, and Group 2 (G2) received a placebo. Randomization was handled by an independent third party using a dedicated randomization software.

Double-Blind Design:

Neither the patients nor the investigators knew the treatment assignment. EVACUR and placebo capsules are identical in appearance.

Treatment:

EVACUR:

A phytotherapeutic compound presented in capsule form. Each bottle contains 40 capsules composed of: Nigella seed, Zinc sulfate, Echinacea, Vitamin C, Red ginseng, Ginger, Chamomile, Spirulina, Royal jelly, Ganoderma, Vitamins B1, B6, B12, Selenium(**Table1**).

Contra-indications: Allergy to any component of the supplement.

Placebo:

Capsules containing starch, packaged identically to EVACUR bottles.

Both treatments will be administered at a dose of 2 capsules per day in the morning (3 bottles per patient for the study duration).

Follow-up:

Patients attended three visits at baseline**M0**, one month**M1**, and two months**M2**. The FACIT score was assessed during each visit along with a physical examination.

Adverse Events:

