Potential side effects will be recorded and evaluated throughout the study. Occurrence of any adverse event will lead to patient exclusion and trigger a pharmacovigilance investigation. All adverse events must be reported immediately to the principal investigator.

Fatigue Assessment Score:**Functional Assessment of Chronic Illness Therapy – Fatigue (FACIT-F)**

A 13-item questionnaire with responses on a Likert scale from 1 (not at all) to 5 (very much).

Total score out of 52; higher scores indicate less fatigue. Can be calculated if at least 50% of the questions are answered.

Reliability: High (Cronbach's alpha = 0.94)

Validity: Strong, with good correlation with other fatigue measurement tools

Completion time: 5–10 minutes

A validated Arabic version is available with good psychometric properties .

Evaluation Criteria:**Primary Endpoint:**

A mean Facit-F score improvement between G1 and G2 at month2 > Minimal Clinically Important Difference(MCID). The MCID in SLE is estimated at 3.4T[5].

Secondary Endpoints:

Improvement in the disease activity SLEDAI score

Good tolerance of the dietary supplement.

Statistical Analysis:

Data were analyzed using SPSS. Appropriate statistical tests will be applied, including Student's t-test or the Wilcoxon test. Randomization will be conducted using dedicated software.

Ethical considerations

This study was conducted according to the Declaration of Helsinki and approved as well by the RABTA hospital's ethics committee under the number of CERB33/2023. Informed consent was given by each patient before starting the study. Each patient will be assigned an inclusion number used for randomization and data entry, ensuring patient confidentiality.

Statements & declarations:

- **Funding:** Wellnet Pharmaceutical Factory ® provided the dietary supplement and the placebo free of charge. No additional funding was required
- **Conflict of Interest:** Wellnet Pharmaceutical Factory® had no role in the study design, data collection, analysis, interpretation, or decision to submit the manuscript for publication.

-Informed consent

Informed consent was obtained from all individual participants included in the study after reading and agreeing with the details of this trial.

- **Availability of data and material :** data are available on request from the authors

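### SLEDAI improvement is a secondary endpoint, but the visit schedule does not secure the month-2 SLEDAI score it needs

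*Protocol*

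**What the plan says.** The title sets out two outcomes: "Assessing the Impact of Herbal Supplement on Fatigue and Disease Activity in SLE". The aim, at the end of the Introduction, covers one of them: it "was to evaluate the efficacy of using herbal-based treatment on patients with SLE-related fatigue".

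Under Evaluation Criteria, the primary endpoint concerns fatigue and gives both a contrast and a time: "A mean Facit-F score improvement between G1 and G2 at month2". Two secondary endpoints follow: "Improvement in the disease activity SLEDAI score" and "Good tolerance of the dietary supplement".

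Measurement of SLEDAI is mentioned once, under Data Collection: "Disease activity was evaluated using clinical SLEDAI-2K score". No visit is attached to that sentence.

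Follow-up sets visits at M0, M1 and M2 and says what is done at them: "The FACIT score was assessed during each visit along with a physical examination". SLEDAI is not named there. Statistical Analysis offers a t-test or a Wilcoxon test and does not tie either to an endpoint.

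**The concern.** An improvement is a difference between two scores, so the endpoint can be assessed only if SLEDAI is scored at baseline and again later. Sites take their visit tasks from the schedule, and this schedule gives them no instruction to score SLEDAI at any visit.

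An unscheduled measurement is a different kind of gap from an unspecified analysis. A statistical analysis plan can define a contrast, a time point or a model after the protocol is written. It cannot create an M2 score that nobody recorded.

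At stake is the disease-activity half of the title. The aim does not mention disease activity and the other secondary endpoint is tolerance, so any statement about disease activity rests on this one line.

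**Working it through.** **1. Visits named for each assessment (Follow-up and Data Collection)**

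| Assessment | M0 | M1 | M2 | Visits named |
|---|---|---|---|---|
| FACIT | yes | yes | yes | 3 of 3 |
| Physical examination | yes | yes | yes | 3 of 3 |
| Clinical SLEDAI-2K | no visit named | no visit named | no visit named | 0 of 3 |

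The endpoint needs a score at no fewer than two of these visits. The text assigns it to none.

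**2. Weight of the endpoint.** There are two secondary endpoints. SLEDAI is the only one of the two that concerns efficacy, and the only endpoint of any rank that concerns disease activity.

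**3. What the protocol lets us size.** There is no protocol figure to reproduce. It gives no sample size, no SLEDAI standard deviation and no M0-M2 correlation, so the effect of a missing M2 score on the SLEDAI result cannot be calculated.

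**4. What baseline adjustment is worth once M0 and M2 scores exist.** This concerns the proposed analysis, not the schedule gap. Assume equal variance s² at M0 and M2, correlation r between them, a linear relation with the same slope in both groups, and write k = 1/n1 + 1/n2. Variance of the G1-G2 difference:

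- plain comparison at M2: s²k
- comparison of change from M0: 2(1 − r)s²k
- comparison at M2 adjusted for M0: about (1 − r²)s²k

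The factor k cancels in every ratio, so the 2:1 allocation does not matter here.

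- Adjusted relative to plain M2: 1 − r²
- Adjusted relative to change: (1 − r²) / [2(1 − r)] = (1 + r)/2

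| Assumed r | 1 − r² | 2(1 − r) | Adjusted ÷ plain M2 | Adjusted ÷ change |
|---|---|---|---|---|
| 0.5 | 0.75 | 1.00 | 75% | 75% |
| 0.7 | 0.51 | 0.60 | 51% | 85% |
| 0.8 | 0.36 | 0.40 | 36% | 90% |

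Because the endpoint is worded as improvement, the change-score column is the more natural reference. On that reference the variance saved is 25%, 15% and 10%. The larger savings in the plain-M2 column apply only if the planned test would have ignored baseline.

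**The case against.** The strongest reply is that this is silence, not error. The word improvement implies a later score. Follow-up does not say that its two assessments are the only ones. In Data Collection the FACIT sentence is labelled as baseline and the SLEDAI sentence is not, so repeated scoring is a fair reading. An examination takes place at every visit and could provide the setting for a clinical score. All of this stands. A reader might infer that SLEDAI was measured only at baseline, and the text does not support that. What remains is that implying a measurement does not schedule it.

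The endpoint line also names no visit and no group contrast, unlike the primary endpoint. A reader might infer that a change within G1 alone is intended. The protocol proposes no such analysis, describes a placebo-controlled trial, and contrasts the groups for its primary endpoint. Visit and contrast may also be defined in an analysis plan that is not shown. This part is secondary.

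Two further inferences should not be drawn. The laboratory sentence ("Biological assessments were performed such as Anti-dsDNA antibody titers, ANA and serum C3 and C4 levels") is undated too, but the protocol names a clinical score and does not list its items, so nothing shows that blood results are needed at M2. The shorter name SLEDAI in the endpoint reads as shorthand for the one instrument that is named, not as a change of version.

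Finally, the title speaks of results and the visits are described in the past tense, so a new scheduling line may come too late. That is a fair limit on the remedy, and the fix below covers both situations.

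**Conclusion.** The point holds in a limited form. A secondary endpoint depends on an M2 score that the visit schedule assigns to no visit (0 of 3, against 3 of 3 for FACIT). A site could comply with Follow-up and leave the endpoint impossible to assess. Whether that happened cannot be told from the protocol, and the consequence for the SLEDAI result cannot be sized.

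This should be corrected, but it does not touch the primary fatigue endpoint, which has its visit and contrast. The finding rests on the text alone. The variance figures rest on assumed correlations, equal variances and a linear model. They support the suggested analysis, and the finding does not depend on them.

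**What to change.** **If visits are still to come.** Add one line to Follow-up: clinical SLEDAI-2K is scored at M0 and M2 by the blinded investigator. Define the endpoint as the G1-G2 difference in that score at M2, adjusted for the M0 score, in place of an unadjusted t-test or Wilcoxon test. The cost is scoring time at a visit that already exists and a standard regression model.

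**If visits are complete.** Add one sentence stating at which visits SLEDAI was scored. Where prospective M0 and M2 scores exist, use the same adjusted comparison. If no prospective M2 score exists, report the endpoint as not assessed and make no disease-activity claim, including in the title. The cost is one sentence or a narrower claim.

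### The tests the protocol names do not adjust for baseline (M0) FACIT-F, which is already collected; ANCOVA would be a cheap, modest gain in precision and not the correction of an error

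*Protocol*

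**What the plan says.** The protocol's Statistical Analysis section has one sentence on methods: "Appropriate statistical tests will be applied, including Student's t-test or the Wilcoxon test". It assigns no test to any endpoint and mentions no covariate.

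The Primary Endpoint is "A mean Facit-F score improvement between G1 and G2 at month2", set against an MCID of 3.4 points. It does not say whether improvement means the M2 score or the change from M0.

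The baseline value is at hand. Data Collection states "Baseline FACIT score was collected", and Follow-up, with visits at M0, M1 and M2, states "The FACIT score was assessed during each visit along with a physical examination". Entry requires "Presence of fatigue, defined as a FACIT-F score < 34", which narrows the spread of M0 scores. Allocation is 2:1.

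The document leaves unclear whether analysis is still ahead. The title reads "Results from an 8-Week Randomized Trial" and the Statistical Analysis section says "Data were analyzed using SPSS", yet the sentence on tests is in the future tense.

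**The concern.** The endpoint is a difference in means of a score that is also measured at baseline. A t-test on M2 scores ignores the baseline. A t-test on change subtracts it in full, which is optimal only if the M2-on-M0 slope is 1. ANCOVA estimates the slope from the data.

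Three things follow from staying with the named tests:

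- **Precision.** The difference set beside 3.4 is estimated somewhat less precisely than the same data allow.
- **Two possible estimates.** The t-test gives different estimates for the M2-score and change-score readings of improvement. ANCOVA with M0 as covariate gives the same treatment effect under both.
- **Chance imbalance.** With slope b, a chance M0 difference between arms carries into the M2-score difference by a factor b, and into the change-score difference by 1-b in the opposite direction.

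If Wilcoxon were used for this endpoint, it would yield no mean difference to compare with 3.4. The text neither states nor excludes that use.

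**Working it through.** The protocol has no figure to reproduce: it states no SD, correlation, sample size, alpha or power.

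**Inputs.** From the protocol: entry at FACIT-F below 34, maximum score 52, 2:1 allocation, threshold 3.4. Assumed: FACIT-F in the source population normal with mean μ = 25, 28, 30, 33 or 36 and SD σ = 10 or 11; M2-on-M0 slope b = 0.3, 0.4, 0.5, 0.6 or 0.7; N = 30, 60 or 90.

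**Model.** M0 is kept if 0 ≤ M0 < 34 and then has variance v. M2 = μ + b(M0 - μ) + e, with Var(e) = σ²(1-b²). Per-patient variances:

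- ANCOVA: σ²(1-b²)
- M2 score: b²v + σ²(1-b²)
- Change: (1-b)²v + σ²(1-b²)

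Estimating the slope multiplies the ANCOVA variance by 1 + 1/(N-4), an added 3.8%, 1.8% and 1.2% at N = 30, 60 and 90.

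**Worked case** (μ = 30, σ = 10, so v = 44.5; N = 60, factor 1.018):

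| b | ANCOVA | M2 score | Change | Net saving vs M2 | Net saving vs change |
|---|---|---|---|---|---|
| 0.3 | 91.0 | 95.0 | 112.8 | 2.5% | 17.9% |
| 0.5 | 75.0 | 86.1 | 86.1 | 11.4% | 11.4% |
| 0.7 | 51.0 | 72.8 | 55.0 | 28.7% | 5.6% |

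For b = 0.5: 1 - 75.0 × 1.018 / 86.1 = 11.4%.

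**Whole grid, net variance saving:**

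| N | vs better unadjusted test | vs change | vs M2 score |
|---|---|---|---|
| 30 | -1% to 12% | 2% to 20% | -1% to 32% |
| 60 | 1% to 14% | 4% to 22% | 1% to 34% |
| 90 | 2% to 15% | 4% to 22% | 2% to 34% |

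The saving against the better test is largest at b = 0.5, where the two unadjusted tests are equally good. It is smallest at b = 0.3, where the M2-score test is already close to ANCOVA. At N = 60 the 95% CI is 0.6%-7.3% narrower than with the better unadjusted test. Its half-width is 4.0-5.8 points with ANCOVA, 4.0-6.5 on change and 4.5-5.9 on M2 scores.

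Simulation of the same model (20,000 trials per setting, μ = 30, σ = 10.5, N = 60) gave net savings against change and M2 scores of 17.5% and 2.4% at b = 0.3, 10.7% and 11.1% at b = 0.5, and 5.2% and 29.0% at b = 0.7. All three estimators were unbiased: mean null differences lay within 0.03 of 0.

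**Slope and correlation differ here.** b equals the correlation before selection. The entry rule narrows M0, so the correlation among enrolled patients is lower: b = 0.5 corresponds to about 0.31-0.40 on this grid, and b = 0.7 to 0.48-0.59. The point at which change scores overtake M2 scores is a slope of 0.5, not an observed correlation of 0.5.

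**Chance imbalance at N = 60 (40:20).** The SD of M0 after selection is 5.6-7.8. The SD of the between-arm M0 difference is √(1/40 + 1/20) × (5.6 to 7.8) = 1.5-2.1 points, and its 95% limits are ±3.0 to ±4.2. Multiplied by b or 1-b (both span 0.3-0.7), a 1-SD imbalance shifts an unadjusted difference by 0.5-1.5 points, and one at the 95% limits by 0.9-2.9.

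**The case against.** The strongest reply is that nothing here is wrong. The word including leaves the list open, no test is assigned to the primary endpoint, and covariate adjustment is a usual item for a statistical analysis plan, which may exist but is not at hand. That stands, and it is why the point is an improvement and not an error. What remains is that the protocol does name methods, and a better one is available from data it already collects.

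The gain is also small where it matters most. The figures above 30% arise only against M2 scores with a steep slope. Improvement more naturally suggests change from M0, and at b = 0.7 the saving over change is only 4%-7% at N = 60. Every 95% half-width above exceeds 3.4 points, so the choice of test would hardly alter what a trial of 60 could show. This too stands. An equal-SD calculation that ignores the entry rule gives 15%-35% over change scores (correlations 0.3-0.7); those figures are too favourable for this trial.

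A reader might infer that the t-test is biased or invalid, that the protocol rules out adjustment, or that it prescribes Wilcoxon for FACIT-F. None of these is supported. Randomisation makes the unadjusted comparison unbiased, the list excludes nothing, and Wilcoxon is linked to no endpoint.

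**Conclusion.** The point holds as a minor efficiency improvement. Neither named test adjusts for M0 FACIT-F. ANCOVA would estimate the primary mean difference with a variance about 1%-14% lower than the better unadjusted test at N = 60, and -1% to 12% lower at N = 30. It also removes the need to guess which unadjusted form is better: a wrong guess at N = 60 costs 13%-22% of variance at slope 0.3 (change scores) or 22%-34% at slope 0.7 (M2 scores).

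These sizes rest on the assumed mean, SD, slope and N, none of which the protocol gives. At a slope near 0.3 and N near 30 there is essentially no net gain over M2 scores (-1% to 2%). The trial's validity is not in question.

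**What to change.** **If the data are still blinded and unanalysed:** name one primary analysis, ANCOVA of M2 FACIT-F on treatment group and M0 FACIT-F. Report the adjusted mean difference (G1 minus G2) with its 95% CI beside the 3.4-point threshold, and leave the endpoint's comparison with 3.4 as it is. Keep an unpaired rank-sum test as a sensitivity analysis only.

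**If the data are already analysed,** as the title and the past-tense wording suggest: leave the reported primary result as it is and add the ANCOVA, labelled post hoc. The protocol assigns no test to the primary endpoint, so it gives no basis for replacing one result with another after the fact.

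**Cost:** a sentence of wording and one SPSS model, with no new data or patients. The statistical price is one degree of freedom, about 4% of variance at N = 30, 2% at N = 60 and 1% at N = 90; this is already deducted in the net figures.
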